Alternative Hypothesis: After accounting for baseline differences, there is a difference in average end-of-life QOC scores between control patients and Best Case/Worst Case intervention patients.

10. For **hospice enrollment during 2-year follow up**, for each treatment arm, we will report the sample counts and percentages. The denominator for each proportion will include all subjects randomized to their respective treatment arm. The treatment effect will be assessed using a LRT of the fixed effect from the logistic mixed-effects model. The logistic mixed-effects model will include a random-intercept for physician, and will include fixed effects for: site, comorbidity, and baseline functional status.

Null Hypothesis: After accounting for baseline differences, there is no difference in the proportion of patients with hospice enrollment between control patients and Best Case/Worst Case intervention patients.

Alternative Hypothesis: After accounting for baseline differences, there is a difference in the proportion of patients with hospice enrollment between control patients and Best Case/Worst Case intervention patients.

11. For **documentation of new advance care planning during 2-year follow up**, for each treatment arm, we will report the sample counts and percentages. The denominator for each proportion will include all subjects randomized to their respective treatment arm. The treatment effect will be assessed using a LRT of the fixed effect from the logistic mixed-effects model. The logistic mixed-effects model will include a random-intercept for physician, and will include fixed effects for: site, comorbidity, and baseline functional status.

Null Hypothesis: After accounting for baseline differences, there is no difference in the proportion of documentation of new advance care planning between control patients and Best Case/Worst Case intervention patients.

Alternative Hypothesis: After accounting for baseline differences, there is a difference in the proportion of documentation of new advance care planning between control patients and Best Case/Worst Case intervention patients.

12. For **treatment intensity at the end of life**, for each treatment arm, we will report the sample counts and percentages of patients who experience any ER visits or ICU stays or hospitalization as determined by chart review or patient or caregiver report within 30-days of death. The denominator for each proportion will include all subjects randomized to their respective treatment arm that died within the study period. The treatment effect will be assessed using a LRT of the fixed effect from the logistic mixed-effects model. The logistic mixed-effects model will include a random-intercept for physician, and will include fixed effects for: site, comorbidity, and baseline functional status.

Null Hypothesis: After accounting for baseline differences, there is no difference in the proportion of treatment intensity at the end of life between control patients and Best Case/Worst Case intervention patients.

Alternative Hypothesis: After accounting for baseline differences, there is a difference in the proportion of treatment intensity at the end of life between control patients and Best Case/Worst Case intervention patients.

13. For **surgical treatment intensity**, for each treatment arm, we will report the sample counts and percentages of patients who experience any surgical procedures within 30-days of death. The denominator for each proportion will include all subjects randomized to their respective treatment arm that died within the study period. The treatment effect will be assessed using a LRT of the fixed effect from the logistic mixed-effects model. The logistic mixed-effects model will include a random-intercept for physician, and will include fixed effects for: site, comorbidity, and baseline functional status.

Null Hypothesis: After accounting for baseline differences, there is no difference in the proportion of surgical treatment intensity between control patients and Best Case/Worst Case intervention patients.

Alternative Hypothesis: After accounting for baseline differences, there is a difference in the proportion of surgical treatment intensity between control patients and Best Case/Worst Case intervention patients.

14. For **initiation of dialysis during 2-year follow up**, for each treatment arm, we will report the sample counts and percentages. The denominator for each proportion will include all subjects randomized to their respective treatment arm. The treatment effect will be assessed using a LRT of the fixed effect from the proportional odds cumulative incidence model for competing risks, incorporating the competing risk of death.⁴⁴ The model will include a random-intercept for physician, and will include fixed effects for: site, comorbidity, and baseline functional status.

Null Hypothesis: After accounting for baseline differences, there is no difference in the proportion of initiation of dialysis between control patients and Best Case/Worst Case intervention patients.

Alternative Hypothesis: After accounting for baseline differences, there is a difference in the proportion of initiation of dialysis between control patients and Best Case/Worst Case intervention patients.

15. For **time to on-study death**, for each treatment arm, we will report survival rates by six month intervals, every 6 months from baseline to 2-years. Risk groups will include all patients all subjects randomized to their respective arms. The treatment effect will be assessed using a LRT of the fixed effect from the logistic mixed-effects model. The mixed-effects Cox regression model will include a random-intercept for physician, and will include fixed effects for: site, comorbidity, and baseline functional status.

Null Hypothesis: After accounting for baseline differences, there is no difference in the 2-year survival rate of on-study death between control patients and Best Case/Worst Case intervention patients.

Alternative Hypothesis: After accounting for baseline differences, there is a difference in the 2-year survival of on-study death between control patients and Best Case/Worst Case intervention patients.

16. For **caregiver-reported Quality of Dying and Death** (QODD) within 3 months of patient death, for each treatment arm, we will report the mean and standard deviation of the QODD composite scores. Only patients who died within the study period will be analyzed in the treatment arms they were randomized. The treatment effect will be assessed using a LRT of the fixed effect from the linear mixed-effects model. The linear mixed-effects model will include a random-intercept for physician, and will include fixed effects for: site, comorbidity, and baseline functional status.

Null Hypothesis: After accounting for baseline differences, there is no difference in average caregiver-reported quality of dying and death scores between control patients and Best Case/Worst Case intervention patients.

Alternative Hypothesis: After accounting for baseline differences, there is a difference in average caregiver-reported quality of dying and death scores between control patients and Best Case/Worst Case intervention patients.

17. For the **Cambridge Palliative Audit Schedule (CAMPAS-R)** caregiver reported health related quality of life, for each treatment arm, we will report the mean and standard deviation in composite score at last follow-up (either 2 years of follow-up or last administered survey prior to death, whichever occurs first). The treatment effect will be assessed using a LRT of the fixed effect from the linear mixed-effects model. The linear mixed-effects model will include a random-intercept for physician, and will include fixed effects for: baseline CAMPAS-R score, site, comorbidity, and baseline functional status.

Null Hypothesis: After accounting for baseline differences, there is no difference in average CAMPAS-R score at last follow-up between control patients and Best Case/Worst Case intervention patients.

Alternative Hypothesis: After accounting for baseline differences, there is a difference in average CAMPAS-R score at last follow-up between control patients and Best Case/Worst Case intervention patients.

18. For **caregiver-reported general Quality of Communication (QOC)** within 48 hours of enrollment, for each treatment arm, we will report the mean and standard deviation of the general 6-item subscale composite scores. The treatment effect will be assessed using a LRT of the fixed effect from the linear mixed-effects model. The linear mixed-effects model will include a random-intercept for physician, and will include fixed effects for: site, comorbidity, and baseline functional status.

Null Hypothesis: After accounting for baseline differences, there is no difference in average general QOC scores between control patients and Best Case/Worst Case intervention patients.

Alternative Hypothesis: After accounting for baseline differences, there is a difference in average general QOC scores between control patients and Best Case/Worst Case intervention patients.

19. For **caregiver-reported end-of-life Quality of Communication (QOC)** within 48 hours of enrollment, for each treatment arm, we will report the mean and standard deviation of the general 7-item subscale composite scores. The treatment effect will be assessed using a LRT of the fixed effect from the linear mixed-effects model. The linear mixed-effects model will include a random-intercept for physician, and will include fixed effects for: site, comorbidity, and baseline functional status.

Null Hypothesis: After accounting for baseline differences, there is no difference in average end-of-life QOC scores between control patients and Best Case/Worst Case intervention patients.

Alternative Hypothesis: After accounting for baseline differences, there is a difference in average end-of-life QOC scores between control patients and Best Case/Worst Case intervention patients.

Exploratory analyses

1. Per-protocol analysis:

The study team will assess adherence to the Best Case/Worst Case intervention using ascertainment and review of the Best Case/Worst Case graphic aid. Primary outcomes for aims 1 through 3 will be repeated removing those in the intervention group that did not adhere to the protocol, specifically removing those who did not receive the Best Case/Worst Case intervention.

2. Heterogeneity of Treatment Effect (HTE):

To determine the impact of the intervention on different subgroups of interest, heterogeneity of treatment effects will be explored. Mixed-effects models with random-intercepts for nephrologist will be fit for each primary outcome in Aim 1 to 3. These models will be fit with a fixed-effect interaction term between intervention status and the following subgroup variables: gender, race/ethnicity (minority/non-minority), health literacy (low/high), age (less than 80/older than 80), insurance status (Medicaid (dual eligible)/no Medicaid), and nephrologist background (MD/advance practice provider (PA/NP)). Significance in interaction fixed-effects will indicate heterogeneity of treatment effect. Caregiver outcomes (secondary analysis outcomes 9-12) will also be explored for HTE in a similar manner.

3. Casual Mediation Analysis:

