This is a multi-site, cluster-randomized clinical trial supported by the infrastructure of the Palliative Care Research Cooperative Group (PCRC). It is a parallel randomization trial with a wait-list control, randomizing nephrologists within each site to receive the intervention at study initiation or after study completion. We will enroll a total of 320 pre-dialysis patients with an estimated glomerular filtration rate (eGFR) of less than 20mL/min/1.73M² who are age 60 and older and have an estimated survival of 18 months or less.³⁶ We expect eight sites are required to ensure complete enrollment (one enrollment plan for example, 8 sites x 4 nephrologists per site with 10 patients per nephrologist = 320). (Note: two sites were added in 2022, for a total of ten sites.) We will follow patients for up to two years after study enrollment. At the start of the study, within each site, nephrologists are randomized to the control or intervention group in a ratio of 1:1. A block randomization scheme will be utilized with blinded block size. Nephrologists assigned to the intervention group will receive training on how to use the Best Case/Worst Case communication tool. Patients in the control group will receive usual care; patients in the intervention group will receive care from their nephrologist trained to use the Best Case/Worst Case communication tool. Palliative care will be available to all patients.

Table: Outcomes Measures for Each Aim				
Construct	Specific Measure	Type; range	Source	Timing
Aim 1: receipt of palliative care and intensity of treatments received at the end of life				
Receipt of palliative care	Any palliative care consult within 12 months of enrollment	Binary; 0/1	Chart review	T0 to 12 mo
Intensity of treatment	ICU admission within 30 days of death	Binary; 0/1	Chart review	T3 minus 30d.
Aim 2: Health-related Quality of Life				
Health related quality of life	Functional Assessment of Chronic Illness Therapy-Palliative Care Version 4 (FACIT-Pal)	Continuous; 0-184	Patient	T2a.... T2h
Aim 3: Quality of Communication				
Quality of Communication	Quality of Communication Questionnaire (QOC)	Continuous; 0-10	Patient	T1
Secondary Outcomes and Follow-up Measures				
Receipt of palliative care	Receipt of any palliative care during study period Hospice enrollment New documentation of advance care planning	Binary; 0/1 Binary; 0/1 Binary; 0/1	Chart review Chart review Chart review	T0 to 2 yr. T0 to 2 yr. T0 to 2 yr.

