Alternative Hypothesis: After accounting for baseline differences, there is a difference in the proportion of patients with an ICU admissions within 30 days of death between control patients and Best Case/Worst Case intervention patients.

3. For the **FACIT-Pal total score patient reported health related quality of life** (score range 0-184, 46 items, survey questions 1-46), for each treatment arm, we will report the mean and standard deviation of the **FACIT-Pal total score at last follow-up** (either 2 years of follow-up or last administered survey prior to death, whichever occurs first). The treatment effect will be assessed using a LRT of the fixed effect from the linear mixed-effects model. The linear mixed-effects model will include a random-intercept for physician, and will include fixed effects for: baseline FACIT-Pal total score, site, comorbidity, and baseline functional status.

Null Hypothesis: After accounting for baseline differences, there is no difference in the average FACIT-Pal total score at last follow-up between control patients and Best Case/Worst Case intervention patients.

Alternative Hypothesis: After accounting for baseline differences, there is a difference in the average FACIT-Pal total score at last follow-up between control patients and Best Case/Worst Case intervention patients.

4. For the **FACIT-Pal total score patient reported healthy quality of life** (score range 0-184, 46 items, survey questions 1-46), for each treatment arm, we will report the mean and standard deviation of the **score slopes** (difference in baseline and either 2 years of follow-up or last administered survey prior to death, whichever occurs first, divided by the length of follow-up). The treatment effect will be assessed using a LRT of the fixed effects from the linear mixed-effects model. The linear mixed-effects model will include a random-intercept for physician, and will include fixed effects for: site, comorbidity, and baseline functional status.

Null Hypothesis: After adjusting for baseline differences, there is no difference in the slope of the FACIT-Pal total score between control patients and Best Case/Worst Case intervention patients.

Alternative Hypothesis: After adjusting for baseline differences, there is a difference in the slope of the FACIT-Pal total score between control patients and Best Case/Worst Case intervention patients.

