5. For the **FACT-G total score patient reported health related quality of life** (score range 0-108, 27 items, survey questions 1-27), for each treatment arm, we will report the mean and standard deviation of the **FACT-G total score** at last follow-up (either 2 years of follow-up or last administered survey prior to death, whichever occurs first). The treatment effect will be assessed using a LRT of the fixed effect from the linear mixed-effects model. The linear mixed-effects model will include a random-intercept for physician, and will include fixed effects for: baseline FACT-G score, site, comorbidity, and baseline functional status.

Null Hypothesis: After accounting for baseline differences, there is no difference in the average FACT-G score at last follow-up between control patients and Best Case/Worst Case intervention patients.

Alternative Hypothesis: After accounting for baseline differences, there is a difference in the average FACT-G score at last follow-up between control patients and Best Case/Worst Case intervention patients.

6. For the **FACIT-Pal palliative care subscale (PalS) patient reported health related quality of life** (score range 0-76, 19 items, survey questions 28-46) for each treatment arm, we will report the mean and standard deviation of the subscale composite scores for **PalS** at last follow-up (either 2 years of follow-up or last administered survey prior to death, whichever occurs first). The treatment effect will be assessed using a LRT of the fixed effect from the linear mixed-effects model. The linear mixed-effects model will include a random-intercept for physician, and will include fixed effects for: baseline Pal score, site, comorbidity, and baseline functional status.

Null Hypothesis: After accounting for baseline differences, there is no difference in the average PalS score at last follow-up between control patients and Best Case/Worst Case intervention patients.

Alternative Hypothesis: After accounting for baseline differences, there is a difference in the average PalS score at last follow-up between control patients and Best Case/Worst Case intervention patients.

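### Secondary outcome 11 (new advance care planning) would be analysed more precisely, at almost no cost, if its model adjusted for planning already documented at enrolment

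*SAP*

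**What the plan says.** The outcomes table lists the measure among the secondary outcomes as "New documentation of advance care planning", a binary variable taken by chart review from enrolment to two years. Item 11 of the secondary outcomes, on "documentation of new advance care planning during 2-year follow up", fixes three things:

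- **Population:** "The denominator for each proportion will include all subjects randomized to their respective treatment arm". Patients with planning already on file are neither excluded nor analysed separately.
- **Model:** "The logistic mixed-effects model will include a random-intercept for physician, and will include fixed effects for: site, comorbidity, and baseline functional status". This is a complete list, and prior ACP is not on it.
- **Hypothesis:** "After accounting for baseline differences, there is no difference in the proportion of documentation of new advance care planning" between the arms.

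For several scores the SAP adds the baseline value of the same measure to these covariates. Item 3 has "fixed effects for: baseline FACIT-Pal total score, site, comorbidity, and baseline functional status", item 5 has "fixed effects for: baseline FACT-G score, site, comorbidity, and baseline functional status" and item 17 has "fixed effects for: baseline CAMPAS-R score, site, comorbidity, and baseline functional status". Item 6, the palliative care subscale, does the same.

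**The concern.** A document can be called new only against what was there before, so ACP status at enrolment is closely tied to this outcome. A patient with a plan on file may have less reason to produce another. Equally, an existing plan may mark a patient who keeps plans up to date. Either way prior ACP is likely to be prognostic, and the person abstracting the chart has to look at it anyway.

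Two things follow if it is left out. The comparison may be less powerful than it could be. And if the arms happen to differ in prior ACP, part of that difference carries into the estimated effect. The randomised units are nephrologists, about 16 per arm (32 / 2), so such differences can be larger than when 320 patients are randomised individually.

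**Working it through.** **Inputs from the SAP.** 320 patients, 160 per arm; 32 nephrologists with 10 patients each on average; 1:1 allocation of nephrologists within site; two-sided alpha 0.05 (Study design; Analysis of Primary Outcome). The SAP states no rate, effect size or power for item 11, so there is no figure to reproduce. Its 80% and 90% power figures concern receipt of palliative care.

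**Assumptions.** The prevalence of prior ACP, the rates of new ACP by prior status and the treatment odds ratio are all assumed and varied. The main runs use a prevalence of 50% and an odds ratio of 2. Design effects are 1.0 (no clustering) and 1 + (10 − 1) × 0.10 = 1.9 (intracluster correlation 0.10).

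**Step 1: size of a chance imbalance in prior ACP.**
- Ignoring clustering: SD = √(2 × 0.5 × 0.5 / 160) = 0.056, or 5.6 points; 95% range ±1.96 × 5.6 = ±11 points.
- With intracluster correlation 0.10: 5.6 × √1.9 = 7.7 points; ±15 points.

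**Step 2: what an imbalance does when there is no treatment effect.** Shift in the arm difference = imbalance × (rate with prior ACP − rate without). For 40% without and 10% with, a 10-point imbalance gives 0.10 × (0.10 − 0.40) = −3 points.

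The rejection rate given that imbalance comes from a normal approximation. For the same case at design effect 1.0:
- Arm rates are 0.40 − 0.55 × 0.30 = 0.235 and 0.40 − 0.45 × 0.30 = 0.265, mean 0.25.
- Critical difference: 1.96 × √(2 × 0.25 × 0.75 / 160) = 0.0949.
- SD of the difference given baseline status: √(2 × (0.5 × 0.09 + 0.5 × 0.24) / 160) = 0.0454.
- Rejection probability: Φ((−0.0949 + 0.03) / 0.0454) + 1 − Φ((0.0949 + 0.03) / 0.0454) = 0.077 + 0.003 = 0.080.

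| New ACP without / with prior ACP | Shift, 10-point imbalance | Rejection, design effect 1.0 / 1.9 | Shift, 15-point imbalance | Rejection, design effect 1.0 / 1.9 |
|---|---|---|---|---|
| 40% / 20% | −2.0 | 6.2% / 5.4% | −3.0 | 8.4% / 6.5% |
| 40% / 10% | −3.0 | 8.0% / 5.9% | −4.5 | 13.7% / 8.8% |
| 40% / 5% | −3.5 | 9.3% / 6.2% | −5.25 | 17.9% / 10.5% |
| 20% / 60% | +4.0 | 9.1% / 6.2% | +6.0 | 17.2% / 10.2% |

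A separate simulation with nephrologist clustering and site-stratified allocation (2,500 null trials per scenario) gave 5.4% to 7.3% rejection among trials with an imbalance of 10 points or more, and 4.6% to 6.0% over all trials. So the overall error rate is held, and the excess arises only in the unlucky draws.

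**Step 3: power without and with prior ACP in the model.** Simulated likelihood ratio tests, 320 patients, 8 sites as fixed effects, no clustering, 3,000 replicates per row:

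| New ACP in controls, without / with prior ACP | Unadjusted | Adjusted |
|---|---|---|
| 40% / 40% | 86.1% | 86.6% |
| 40% / 20% | 82.6% | 84.4% |
| 40% / 10% | 69.7% | 76.1% |
| 40% / 5% | 60.3% | 71.1% |
| 20% / 60% | 72.4% | 81.0% |

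Shorter runs at prevalences of 30%, 50% and 70% showed the same pattern, with a largest gain of about 12 points at 40% / 5%. A second simulation with nephrologist clustering but no site terms (odds ratio 2.2, 640 trials per scenario) gave 72.0% to 79.5%, 73.0% to 79.7% and 75.8% to 80.3% for strong associations, and 79.5% to 81.9% for a weak one. Adjustment did not lower power beyond simulation noise in any scenario.

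**The case against.** The strongest reply is that nothing here is wrong. Any randomised comparison that omits a prognostic variable can meet a chance imbalance, and alpha already covers it. Step 2 confirms this, and the point stands.

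Three stronger readings are tempting, and the SAP does not support them:

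- **That item 11 contradicts the SAP's own practice.** Items 3, 5, 6 and 17 are scores measured on the same scale at baseline. Item 11 is an event counted from enrolment, and prior ACP is a different variable. The other event outcomes, including the primary one and items 1, 10 and 14, use the same three covariates. The phrase about baseline differences recurs in nearly every hypothesis and promises nothing about prior ACP. Those scores show that the SAP accepts this kind of adjustment, and no more.
- **That a patient with a complete plan on file is scored as a failure.** The SAP does not define what counts as new. It assigns abstraction rules to a separate abstraction protocol and data dictionary (Blinding), which are not at hand. An updated plan may count.
- **That the odds ratio is biased toward 1.** A logistic model without the covariate estimates a less conditional odds ratio, which is a different quantity and not an error.

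It is also fair to say that the power loss rests on rates the SAP does not give, that the largest gains need an extreme contrast (40% against 5%), and that randomising within site limits imbalance where ACP habits differ mainly between sites.

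What survives is the case for precision: a probable predictor, readable from a chart already under review, is left out of a covariate list fixed in advance.

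**Conclusion.** The point holds as a low-severity improvement. The test in item 11 is valid, with overall type I error near 0.05. Omitting prior ACP may cost about 0 to 11 points of power (about 12 in the most extreme short run), and close to nothing if prior ACP predicts new ACP only weakly. With no true effect, a 10-point imbalance moves the arm difference by about 2 to 4 points, with conditional rejection of about 5–9%.

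These sizes depend on assumed ACP rates, odds ratios and clustering. The direction of the association is unknown, but the benefit of adjusting does not depend on it. A reader might infer that the comparison is systematically biased. The documents do not show that: the distortion is conditional on an unlucky draw. This is one of 19 secondary outcomes, and no power is claimed for it.

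**What to change.** In item 11, add to the logistic mixed-effects model a yes/no fixed effect for ACP documented in the chart at enrolment, keeping the physician random intercept and the three existing covariates. Report the counts and percentages of new ACP by arm within each level of that variable as well as overall. Fixing this before the data are seen avoids a post hoc choice if the arms turn out to differ.

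The cost is one yes/no field from a chart already being abstracted, one degree of freedom and a line of SAP text. No extra patients or visits are needed. The reported odds ratio becomes conditional on prior ACP. If the association is weak, little is gained.

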Teaching nephrologists to use the Best Case/Worst Case communication tool has potential to increase receipt of palliative care and reduce intensive treatments at the end of life via multiple pathways. (Figure 3): first, via direct

provision of information about prognosis and health trajectory, second, through improving the quality of communication about options and outcomes, and third, via improving decision making about dialysis

initiation. Our primary outcome is receipt of palliative care and intensity of treatment at the end of life. We will assess whether patients' palliative care needs were met by measuring the patient's change in health-related quality of life over time. We will measure the impact of upstream outcomes and events that may mediate receipt of palliative care including patient and caregiver-reported assessment of quality of communication and the patient's decision to initiate or forgo dialysis.

[figure not shown]

Figure 3: Theoretical framework behind the Best Case/Worst Case intervention and this proposal

Specific aims

- Aim 1: To test the effect of the Best Case/Worst Case intervention on (1) receipt of palliative care and (2) intensity of treatment at the end of life for older patients with ESRD. We will compare (1) receipt of palliative care within 12 months of enrollment and (2) intensive care unit admissions, hospitalizations and emergency department visits in the last 30 days of life. Receipt of palliative care is the primary outcome for this study.
- Aim 2: To test the effect of the Best Case/Worst Case intervention on quality of life of older patients with ESRD. We will use the Functional Assessment of Chronic Illness Therapy – Palliative Care scale to measure quality of life at baseline, and every three months for up to two years after study enrollment.
- Aim 3: To test the effect of the Best Case/Worst Case intervention on the quality of communication between nephrologists and patients. We will use the Quality of Communication scale, which includes measurement of end-of-life communication. We will also use this patient and caregiver-reported measure to explore the mediating effect of provider communication on downstream health outcomes.

Study design

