Intensity of treatment	ER visit, ICU or hospitalization within 30 days of death Surgical procedures within 30 days of death	Binary composite; 0/1 Count	Chart review Chart review	T3 minus 30d. T3 minus 30d.
Dialysis	Initiation of dialysis, Withdrawal of dialysis	Binary; 0/1	Chart review	T0 to 2 yr.
Death	Patient death	Time to event	Chart review and family report	T3
Bereavement	Quality of Dying and Death (QODD) survey	Continuous; 0-100	Caregiver	T4
Health related quality of life	Cambridge Palliative Audit Schedule (CAMPAS-R) (Caregiver QOL)	Continuous; 0-100	Caregiver	T2a.... T2h
Quality of Communication	Quality of Communication Questionnaire (QOC) (Family member version)	Continuous; 0-10	Caregiver	T1
Practitioner Opinion Survey	Nephrologist perceptions of the communication tool	Continuous; 0 - 15	Nephrologist	Study Completion

mo. = months, yr. = year, d. = day, T0 = enrollment, T1 = 48 hours after enrollment, T2 is every 3 months for up to 2 years, 2_a-2_h = repeated measures every 3 months, T3 = patient death, T4 = 3 months after patient death.

Blinding

Patients and caregivers will be blinded to the objectives of this study. They will be told that the study goal is to evaluate doctor-patient communication. Nephrologists will not be blinded to study group. We will inform all participating nephrologists about the goals of this study. Specifically, this is a study testing an intervention to improve communication about dialysis initiation and to support patient access to palliative care. We will make every effort to blind study staff, yet it is impossible to ensure that study staff will be completely blinded to intervention group. To reduce the possibility of study staff exposure to the nephrologist's randomization assignment we will coordinate the intervention allocation centrally through UW and provide regular reminders to nephrologists that they should avoid revelation of their training to study staff. To decrease ascertainment bias, study staff will adhere to a strict study script during interactions with nephrologists and during survey administration with patients and caregivers. To standardize chart abstraction, we will create a detailed abstraction protocol with data dictionary, and the UW team will train study staff to use the REDCap electronic database. We will ensure data quality by

independent abstraction and double data entry of 10% by the site PI or a suitable designee. We will compare the two abstractions and correct and retrain as needed.

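### Does the exploratory per-protocol analysis need changing because it drops non-recipients from the intervention arm only?

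*SAP*

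**What the plan says.** Under Exploratory analyses, item 1 (Per-protocol analysis), adherence is judged "using ascertainment and review of the Best Case/Worst Case graphic aid". "Primary outcomes for aims 1 through 3 will be repeated" after "removing those in the intervention group that did not adhere to the protocol, specifically removing those who did not receive" the intervention. No corresponding exclusion is made among controls, no date is set by which the aid must exist, and no weighting or complier estimate is named.

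Other parts of the SAP bear on this:

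- Study design: "Patients in the control group will receive usual care", while "patients in the intervention group will receive care from their nephrologist trained to use the Best Case/Worst Case communication tool". Nephrologists are randomised within site.
- Blinding: nephrologists know their assignment.
- General Analysis Plan, Primary Outcome: the denominator is everyone randomised to the arm. The model adjusts for site, comorbidity and baseline functional status, with a random intercept for physician.
- Outcomes table footnote: quality of communication is measured at T1, where "T1 = 48 hours after enrollment".

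**The concern.** A graphic aid can exist only after randomisation and only in the trained arm. Whether one is drawn depends on an unblinded nephrologist and on the patient's condition and openness to the conversation. If those who receive it differ in prognosis or in their inclination towards palliative care, randomisation no longer protects the comparison. A patient who dies before an aid is drawn leaves one arm only. An aid drawn after the 48-hour communication survey, or after a palliative care consult, could still count as receipt.

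The harm would be one of interpretation. Placed beside the all-randomised result, the per-protocol result could be taken as the effect of actually using the tool, when it mixes that effect with selection of unknown sign.

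**Working it through.** The SAP states no figure for this analysis, so there is none to reproduce. The inputs taken from Analysis of Primary Outcome are a 10% baseline consult rate, 80% deaths over two years, 160 patients per arm, a target difference of 10 to 15 points, and 12.9 points detectable with 80% power. The non-receipt share f, the consult rate q of non-recipients without the tool, and the effect d of training on non-recipients are assumptions.

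**1. Selection error with no true effect.** The whole arm has rate 10% = (1 − f)·r + f·q, where r is the rate in those kept. Hence r − 10% = f/(1 − f) × (10% − q).

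| f | q = 5% | q = 10% | q = 15% |
|---|---|---|---|
| 10% | +0.6 | 0 | −0.6 |
| 20% | +1.3 | 0 | −1.3 |
| 30% | +2.1 | 0 | −2.1 |
| 40% | +3.3 | 0 | −3.3 |

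Entries are percentage points. At f = 30%, a nominal 5% two-sided test would reject in about 8.5% (q = 5%) to 9.5% (q = 15%) of trials, and in 18% to 26% at the extremes q = 0 and q = 20% (errors of ±4.3 points). These rates ignore clustering and covariates. The formula is a crude mixture: adjustment for site, comorbidity and functional status would reduce the error so far as those variables capture the selection.

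**2. Timing of receipt.** With 80% dead by 24 months, a constant death hazard is ln(5)/24 = 0.0671 per month. A consult hazard of 0.0130 per month then gives a 10% cumulative incidence at 12 months with death competing. If the aid is drawn by the 48-hour survey, 0.44% have already died. Removing them shifts the 12-month rate by +0.04 points; also removing earlier consults shifts it by −0.03. Errors of a point or more appear only if first use is assumed to come months later (at three months, +1.8 and −1.7). That fits poorly with an outcome on communication measured at 48 hours.

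**3. Would a complier-average estimate be better?** Let e be the effect in recipients. The all-randomised contrast is (1 − f)·e + f·d. Dividing it by the receipt rate gives e + f/(1 − f) × d, so the error is f/(1 − f) × d. At f = 30% that is 0.9 points for d = 2 and 2.1 for d = 5. The bias is smaller than that of the exclusion analysis only when |d| < |10% − q|.

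A simulation compared the two (20,000 runs per case; the SAP's example layout, "8 sites x 4 nephrologists per site with 10 patients per nephrologist"; f = 30%; e = 12.9 points; latent intraclass correlation 0.10, an assumed reading of the SAP's between-physician variance of about 10%):

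| | Largest bias | SD |
|---|---|---|
| Exclusion analysis | 2.2 | 5.2 to 5.5 |
| Complier estimate | 2.2 (0 when d = 0) | 6.5 to 6.8 |

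Root mean squared error for the exclusion analysis is at most √(2.2² + 5.5²) = 5.9 points. For the complier estimate it is at least 6.5, even with no bias. The SAP's analysis has the smaller total error in every case simulated.

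**The case for a change.** The strongest case for a change is that the SAP itself fixes the exclusion rule, sets no date for receipt and gives no caveat, in a population with high expected mortality. A sentence calling the result non-causal, with a table of those removed by nephrologist, would cost almost nothing. A complier estimate has the further merit of being zero when assignment has no effect, which the exclusion analysis cannot promise.

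The structural point stands: the comparison is not randomised, and its bias could take either sign. The null-preserving property of the complier estimate is also real. Its other requirement, however, is that training acts only through use of the tool. The SAP's rationale expects training to increase palliative care and "reduce intensive treatments at the end of life via multiple pathways", and every intervention patient is cared for by a trained nephrologist, so an effect on non-recipients is plausible. Choosing between the two is therefore a choice of estimand and of which error to accept. Requiring the aid to predate each outcome would also give each outcome its own complier population.

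The label and table would be good reporting practice, but they alter no estimate, test or decision. The SAP nowhere calls this analysis confirmatory or causal, and a competent report would give the number removed in any case.

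**Conclusion.** No change to the plan follows. The one-sided removal is real and the resulting contrast can be biased either way. It is also largely inherent in a per-protocol analysis against usual care, since controls have no receipt to assess. Under the assumed ranges (10% to 40% non-receipt, non-recipients 5 points from the 10% baseline) the unadjusted error is 0.6 to 3.3 points. That is below the 10 to 15 points of interest and below the analysis's own simulated sampling SD of 5.2 to 5.5 points at 30% non-receipt. The timing component is about 0.04 points if the tool is used by the 48-hour survey.

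These sizes rest on assumed f, q and d; greater non-receipt or stronger selection would give larger errors. The conclusion does not depend on them alone. The primary outcome is analysed in all randomised patients, this analysis is already exploratory, and the available alternative exchanges one untestable assumption for another with less precision. It is a fair trade-off: readers should treat the per-protocol result as descriptive, which its place in the plan already implies.
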